### 7.1.2 Randomization

Eligible patients will be randomly assigned to study treatment in IWRS on or before the baseline visit. Baseline/Study Day 1 is defined as day the before conditioning begins for patients randomized to the DP arm and the day that conditioning begins for patients randomized to the BSC arm.

For patients whose HSCT/conditioning is postponed after the patient has been screened and randomized but before starting in the study/study treatment:

- If the date of the next planned transplant is >30 days from last screening test, clinical laboratory tests (including for bilirubin values), and ultrasound need to be repeated, and patient eligibility for inclusion in the study needs to be re-assessed before the next planned date for HSCT. Please see additional guidance below:
  - If the patient is no longer eligible then the patient needs to be removed from the study via early termination and the reason for the early termination needs to be clearly documented.

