## 6.9 Removal of Patients from the Study or Study Drug

### 6.9.1 Handling of Early Terminations

All patients are free to withdraw from participation in this study at any time, for any reason, and without prejudice. The investigator must withdraw any patient from the study if the patient states that he/she wants to stop participating in the study. In addition, the investigator, the Sponsor, or its designee, may remove a patient from the study at any time and for any reason. Reasons for early termination from the study or study drug may include the following:

- Withdrawal of consent by patient or patient's parent/legal guardian or representative
- Adverse event which in the opinion of the investigator contraindicates continuation in the study
- Investigator considers it not in the patient's best interest to continue in the study
- Death
- Disease relapse
- Non-compliance with study drug
- Pregnancy
- Sponsor (or its designee) decision to terminate study

The specific reason for the discontinuation from study or study drug should be documented on the termination eCRF. If a patient or patient's parent/legal guardian or representative

Defibrotide (JZP-381)  
Clinical Trial Protocol: 15-007 Version 4.0

Jazz Pharmaceuticals, Inc.  
20 August 2018

---

withdraws informed consent, the specific reason for withdrawing the informed consent should be stated. It is vital to obtain follow-up data on any patient who discontinued study drug because of an AE.

Adverse events resulting in termination will be followed to the satisfactory resolution and determination of outcome as ascertained by the investigator (and/or the Sponsor or its designee). The data will be recorded on the appropriate eCRF.

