## 7.2.1 Assessments During Hospitalization

Hospitalization for patients in both the DP and BSC arms is from Study Day 1/baseline through hospital discharge. Patients must undergo Day +15 post-HSCT assessments before hospital discharge. If discharge occurs earlier (before Day +15 post-HSCT), patients must undergo the Day +15 post-HSCT assessments as close to the day of discharge as possible. If a patient is discontinued early from study/study drug (prior to Day +15 post-HSCT), the Day +15 post HSCT assessments must be completed on the day of study/study drug discontinuation (+1 day).

### 7.2.1.1 Baseline/Study Day 1

The following procedures will be performed or information will be collected at baseline.

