10.1 Analysis of Primary Endpoint

The primary efficacy endpoint is VOD free survival by Day +30 post-HSCT. An event for the primary efficacy endpoint is defined as VOD diagnosis (as assessed by EPAC) or death, whichever is earlier, up to Day +30 post-HSCT.

The time to event for the primary efficacy endpoint will be measured in days and will be calculated as described in Section [8.2.4](#) with the event date equal to the date of VOD diagnosis by EPAC, the date of death up to Day +30 post-HSCT, or the censoring date if no VOD or death occurred.

Subjects will be censored under the following conditions:

- No event by Day +30 post-HSCT:
 - If EPAC makes an assessment of ‘No VOD’ and the subject is still alive at Day +30 post-HSCT, the censoring date will be defined as earliest date of the last assessments available for the modified Seattle criteria components (total bilirubin, weight gain or ascites evaluation, hepatomegaly evaluation) or the last biopsy assessment, whichever is later. Only assessment dates occurring on or before Day+30 post-HSCT will be taken into consideration when censoring.
 - If the subject is still alive at Day +30 post-HSCT and has EPAC-assessed VOD after Day +30 post-HSCT, the censoring date will be Day +30 post-HSCT.
- Not evaluable by Day +30 post-HSCT:
 - If the EPAC makes an assessment of ‘Not Evaluable’ and the subject has not died by Day +30 post-HSCT, the censoring date will be defined as the last date at which VOD could be evaluated (as specified by the EPAC).
 - If the EPAC indicates the last date at which VOD could be evaluated is prior to HSCT, the censoring date will be Day +1 post-HSCT.
- Event occurs prior to HSCT:
 - If the EPAC indicates the date of VOD onset is prior to Day +0 post-HSCT or if the subject dies prior to Day +0 post-HSCT, the censoring date will be Day +1 post-HSCT because the subject was not at risk at the start of the observation period.
- Subject does not undergo HSCT:
 - The date of randomization will be used as Day +0 post-HSCT. The censoring date will be Day +1 post-HSCT.
- Rescue treatment:
 - If a subject in the BSC arm receives rescue treatment with defibrotide but VOD (as assessed by investigator) is not confirmed by EPAC (either EPAC made an assessment of ‘No VOD’ or ‘Not Evaluable’ by Day +30 post-HSCT or the EPAC

made an assessment of VOD but the VOD date is more than 3 days later than the rescue initiation date), the subject will be censored at the date of rescue initiation.

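### Randomised patients must (Protocol 7.1.2) or may (6.9.1) be taken out of the study with no later VOD or survival follow-up, which opens the ITT comparison to informative censoring

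*Protocol*

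**What the plan says.** - **Protocol 7.1.2.** This covers patients already randomised, but not yet started, whose transplant or conditioning is put off. If the new date is more than 30 days after the last screening test, laboratory tests and ultrasound are repeated and eligibility is judged again. On failure: "If the patient is no longer eligible then the patient needs to be removed from the study via early termination". Assignment is open-label (Protocol 5.4), so the arm is known.
- **Protocol 6.9.1.** The investigator, sponsor or designee "may remove a patient from the study at any time and for any reason". One list serves both kinds of exit: "Reasons for early termination from the study or study drug may include the following". It includes "Disease relapse" and "Non-compliance with study drug". Continued data collection is stressed in one case only: "It is vital to obtain follow-up data on any patient who discontinued study drug because of an AE".
- **At exit.** Protocol 7.3.3 provides an early-termination visit that records VOD and survival status. Protocol 7.2.1 brings the Day +15 assessments forward to the time of discontinuation.
- **Analysis.** The ITT set is everyone randomised (Protocol 9.4, SAP 6.2). Early leavers contribute up to censoring (Protocol 9.5), placed at their most recent VOD evaluation (Protocol 9.8.1, SAP 10.1). For subjects who do not undergo HSCT, SAP 10.1 states: "The date of randomization will be used as Day +0 post-HSCT. The censoring date will be Day +1 post-HSCT".
- **Safeguard.** SAP 10.1.1.1 (Sensitivity Analysis I) is a worst case. Subjects terminated early, with the last VOD assessment before Day +23 and no event, count as events in the DP arm and as censored in the BSC arm.

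**The concern.** An ITT analysis needs outcomes on everyone randomised, whether or not they stay on treatment. Here patients stay in the ITT set by name, but the plan stops looking for their outcomes once they are removed from the study. Censoring them is harmless only if leaving is unrelated to risk, and the listed reasons make that doubtful:

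- The re-check in 7.1.2 repeats laboratory tests that include bilirubin, which is both a qualifying liver risk factor (Protocol 4.1) and a VOD criterion.
- Protocol 1.5 lists relapse among the causes of early death, and death is half of the composite endpoint.
- During prophylaxis, non-compliance with study drug can arise only in the DP arm.

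These decisions are taken unblinded, and a blinded adjudication committee cannot judge data that were never collected. At stake are the primary comparison at Day +30 and the key secondary at Day +100, where there is more time for relapse-related exits.

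**Working it through.** **1. The plan's own figures (Protocol 9.3, SAP 4.6).**
- Hazard ratio: ln(0.86)/ln(0.72) = 0.459, as stated (0.46).
- Size: 180/(1 − 0.10) = 200 per arm, as stated.
- A simulation of the two-look design (280 + 120 patients, boundaries 3.2905 and 1.9603, 10% fully lost) gives 90.8% power and 68.2 events on average, against 90% and 68 stated. Exponential event times and futility judged on the current trend are assumptions of this check.

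The sample size reproduces and already allows for dropout.

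**2. What happens to a removed patient.**
- Removed after transplant: an event before removal counts. Later VOD or death is not sought, and the patient is censored at the last VOD evaluation.
- Removed before transplant, with no transplant recorded on study: Day +0 is randomisation and censoring is at Day +1, so the patient contributes essentially nothing.

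**3. Possible effect on type I error (shares and risks assumed).** The documents give only 10% dropout, not split by cause or arm, and fewer than 2% without HSCT. Take the null case: 28% event risk in both arms (the planned BSC rate), 200 per arm. A share d of DP patients only is removed, with k times average risk and no observed events.
- Observed DP rate: p = (0.28 − d·k·0.28)/(1 − d)
- Apparent HR = ln(1 − p)/ln(0.72)
- Observed events D = 200(1 − d)p + 200 × 0.28
- Type I error = Φ(−ln(HR)·√(D/4) − 1.96)

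Example, d = 5% and k = 2: p = 0.252/0.95 = 0.2653; HR = 0.938; D = 50.4 + 56 = 106.4; shift = 0.0637 × 5.16 = 0.33; error = Φ(−1.63) = 0.051.

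| DP share removed | k = 1 | k = 1.5 | k = 2 | k = 2.5 |
|---|---|---|---|---|
| 2% | 0.025 | 0.029 | 0.033 | 0.039 |
| 5% | 0.025 | 0.036 | 0.051 | 0.071 |

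This is a fixed-design normal approximation. The upper end is demanding: 2.5 × 28% means 70% of removed patients would have had an event. With k below 1 the error falls below 0.025. Equal removal at equal relative risk in both arms gives HR 1 and no distortion.

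**4. What Sensitivity Analysis I can show.** Under the planned effect, with removed DP patients counted as events, the DP rate is 0.14(1 − d) + d: 15.7% at d = 2% and 18.3% at d = 5%. Two-proportion power against 28%, 200 per arm, falls from 93% with no removals to about 85% and 63%. A failed worst case would therefore not distinguish bias from a real effect.

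**5. Full follow-up.** Expected events at full enrolment are 400 × 0.21 = 84, against 360 × 0.21 = 75.6. Schoenfeld power at HR 0.46 is 94.5% against 92.2%. This is an upper limit, since consent withdrawals would remain. The gain is mainly in validity, not power.

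**The case against.** The case for leaving the plan alone is substantial.

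- **A worst-case analysis is pre-specified**, and it penalises the DP arm. This stands, and any account of the issue should mention it. But it bounds uncollected outcomes and does not replace them. It is written for Day +30, and SAP 10.2.1 lists no Day +100 counterpart.
- **The mandatory removal is narrow.** It needs a postponement, a gap over 30 days and a failed re-check, and it applies to both arms. This stands. A patient might also fail because liver values improved, which would suggest lower risk, so the direction is open.
- **A reader might infer that relapse or non-compliance forces patients out of the study.** Protocol 6.9.1 only lists possible reasons, and for either kind of exit. Relapse is itself monitored to Day +180. Non-compliance has little scope: site personnel give the drug (5.8), schedule adjustments are tolerated (5.2.1), and discharge before 21 days is not a violation (1.3). The text permits removal and no more.
- **A reader might infer that transplanted patients are censored at Day +1 under the no-transplant rule.** That rule covers only subjects who do not undergo HSCT, and SAP 8.2.3 already sets Day +0 as the day of transplant. The gap is that nobody is told to collect the date, or anything after it, once a patient is removed.
- **Adverse event recording might capture deaths.** Protocol 6.8.1.5 sets a Day +60 minimum but does not say that it continues after removal from the study. For patients without HSCT it ends at early termination. Even read generously, it does not supply VOD components or reach Day +100.
- **Little missing data is expected** (Protocol 9.5). That is an expectation, and the removal wording works against it.

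**Conclusion.** The gap is real and limited. Removal from the study is mandatory in one situation after open-label randomisation and permitted in others, and no passage requires VOD or survival follow-up afterwards. Outcomes that sites could keep collecting are lost, so the ITT comparison is open to informative censoring.

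Its size and direction cannot be established from the documents. The range of about 0.03 to 0.07 for 1-sided type I error rests on assumed DP-only removal of 2 to 5% at 1.5 to 2.5 times average risk, which is deliberately unfavourable; the figure stays at 0.025 if removal is unrelated to risk. It would be wrong to read the 10% dropout allowance as drug-related DP removals, since it is an overall sample-size allowance. It would also be wrong to conclude that a bias towards DP is shown, or that the sample size is in error. This is a cheap improvement.

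**What to change.** In Protocol 7.1.2 and 6.9.1, separate ending study treatment from ending study follow-up. Randomised patients who lose eligibility, relapse or are non-compliant remain in follow-up for transplant date, VOD components and survival to Day +30, +100 and +180 unless consent is withdrawn, and their events count in the ITT analysis. Whether they receive study treatment is left to the existing clinical rules.

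The SAP time-zero rule needs no change: 8.2.3 uses the transplant date once it is collected. Patients never transplanted stay under the present Day +1 rule, which is outside this point.

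The cost is a protocol wording change and follow-up of a small number of extra patients, mostly from routine post-transplant care.

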## 7.2 Treatment Period (DP and BSC Arms); Baseline/Study Day 1 Through Day +30 Post-HSCT

The treatment period for the study is from Study Day 1/baseline through Study Day +30 post-HSCT. Baseline/Study Day 1 is defined as the day before conditioning begins for patients randomized to the DP arm and the day that conditioning begins for patients randomized to the BSC arm.

Best supportive care will be administered to all patients enrolled in the study, beginning on the day prior to conditioning for patients in the DP arm and on the day of conditioning for patients in the BSC arm.

For patients randomized to DP arm, defibrotide prophylaxis will be administered in addition to BSC beginning the day before the first day of the conditioning regimen (Study Day 1) for a recommended minimum of 21 days (corresponding to approximately Day +15 post HSCT) and will end no later than Day +30 post-HSCT.

For patients randomized to the BSC arm, BSC will be administered starting on the day of conditioning (Study Day 1) and continue until Day +30 post HSCT or hospital discharge, whichever occurs earlier.

Defibrotide (JZP-381)  
Clinical Trial Protocol: 15-007 Version 4.0

Jazz Pharmaceuticals, Inc.  
20 August 2018

## 7.2.1 Assessments During Hospitalization

Hospitalization for patients in both the DP and BSC arms is from Study Day 1/baseline through hospital discharge. Patients must undergo Day +15 post-HSCT assessments before hospital discharge. If discharge occurs earlier (before Day +15 post-HSCT), patients must undergo the Day +15 post-HSCT assessments as close to the day of discharge as possible. If a patient is discontinued early from study/study drug (prior to Day +15 post-HSCT), the Day +15 post HSCT assessments must be completed on the day of study/study drug discontinuation (+1 day).

### 7.2.1.1 Baseline/Study Day 1

The following procedures will be performed or information will be collected at baseline.

#### **PRE-DOSE (BEFORE THE START OF STUDY TREATMENT):**

These assessments should be performed pre-dose for patients in the DP arm and before the start of conditioning for patients in the BSC arm.

- Updates to prior medications (i.e., from the time of screening and all prior therapies for underlying disease)
- Review of planned conditioning regimen and GvHD prophylaxis
- Physical examination, including assessments of the skin, head, eyes, ears, nose, throat, neck, thyroid, lungs, heart, abdomen (with palpation of the liver; and with measurement of abdominal girth for pediatric patients only), lymph nodes, extremities, and a general assessment (including edema). Whenever possible, assessment of right upper quadrant pain will be performed.
- Weight. NOTE: Weight can be measured up to 3 days prior to baseline visit. However, this will need to be re-measured at baseline visit in order to record baseline weight.
- Vital signs (blood pressure, pulse, respiratory rate, and body temperature)
- Karnofsky PS ( $\geq 16$  years of age)
- Lansky PS ( $< 16$  years of age)
- EQ-5D-5L (adult patients only)
- EQ-5D-Y (pediatric patients and parents [proxy version 1])
- Clinical laboratory tests (serum chemistry, hematology, and coagulation)
- Calculation of CrCl (using Cockcroft-Gault for adults and Schwartz formula for pediatric patients). If cystatin C is measured, GFR will be calculated using either the Grubb or Larsson formula.
- \*Biomarker blood sample (see [Section 6.6.1](#) for details)
- Immunogenicity sample (DP and BSC arms, see [Section 6.7.1](#) for details)

\*Note: Biomarker sampling can be eliminated if the investigator believes such sampling will compromise patient safety by exceeding daily or monthly blood draw maximums or cause need for transfusion ([Appendix 6](#)).

Defibrotide (JZP-381)  
Clinical Trial Protocol: 15-007 Version 4.0

Jazz Pharmaceuticals, Inc.  
20 August 2018

---

**START OF STUDY TREATMENT:**

- Administration of defibrotide 25 mg/kg/day, given as 4 2-hour infusions of 6.25 mg/kg every 6 hours. Each dose (infused over a 2 hour  $\pm$ 15 min infusion period) may be administered within  $\pm$ 1 hour of the scheduled dosing time provided that there is at least a 2-hour window between the end of an infusion and the start of the next infusion (if randomized to DP arm) or administration of BSC medication(s) (if randomized to BSC arm)
- Patients randomized to DP arm only: Vital signs (blood pressure, pulse, respiratory rate, and body temperature), and intensive monitoring of vital signs only during the first 2 infusions of defibrotide prophylaxis, as follows: 15, 30, 60, and 120 minutes ( $\pm$  5minutes) following start of infusion and at 15 minutes ( $\pm$  5minutes) following the end of the first and second infusions

**POST DOSE (AFTER THE START OF STUDY TREATMENT):**

- Hospitalization information (i.e., dates of hospitalization, dates in ICU, dates of readmission) and inpatient resource use
- Concomitant medications (including actual conditioning and GvHD prophylaxis)
- Monitoring of AEs
- Survival status

**7.2.1.2 Assessments Beginning on Study Day 2, After the Start of Study Treatment****DAILY DURING HOSPITALIZATION**

- Physical examination, including assessments of the skin, head, eyes, ears, nose, throat, neck, thyroid, lungs, heart, abdomen (with palpation of the liver; and with measurement of abdominal girth for pediatric patients only), lymph nodes, extremities, and a general assessment (including edema). Whenever possible, assessment of right upper quadrant pain will be performed
- Weight
- Vital signs (blood pressure, pulse, respiratory rate, and body temperature)
- Clinical laboratory tests (serum chemistry, hematology, and coagulation). Note: bilirubin must be assessed daily during hospitalization; other serum chemistry and hematology tests may be performed a minimum of 3 times weekly and coagulation parameters may be assessed a minimum of once weekly at the discretion of the investigator, to ensure patient safety (see [Appendix 6](#) and [Section 7](#) for details).
- Calculation of CrCl (using Cockcroft-Gault for adults and Schwartz formula for pediatric patients). If cystatin C is measured, GFR will be calculated using either the Grubb or Larsson formula.
- Hospitalization information (i.e., dates of hospitalization, dates in ICU, dates of readmission) and inpatient resource use
- Administration of defibrotide 25 mg/kg/day, given as 4 2-hour infusions of 6.25 mg/kg every 6 hours. Each dose (infused over a 2 hour  $\pm$ 15 min infusion period) may be administered within  $\pm$ 1 hour of the scheduled dosing time provided that there is at least a

Defibrotide (JZP-381)  
Clinical Trial Protocol: 15-007 Version 4.0

Jazz Pharmaceuticals, Inc.  
20 August 2018

2-hour window between the end of an infusion and the start of the next infusion (if randomized to DP arm) or administration of BSC medication(s) (if randomized to BSC arm)

- Concomitant medications (including actual conditioning and GvHD prophylaxis)
- Monitoring of AEs
- Survival status

#### **TWICE WEEKLY DURING HOSPITALIZATION**

- After HSCT only: Acute GvHD (i.e., rash, total bilirubin, stool output)
- Monitoring for VOD (i.e., total bilirubin, hepatomegaly, ascites, weight gain, biopsy [as applicable])
- Monitoring for VOD-associated MOD (i.e., serum creatinine/CrCl or GFR [optional]/dialysis and supplemental oxygen/ventilator support)

#### **WEEKLY DURING HOSPITALIZATION**

- After HSCT only: Neutrophil and platelet engraftment/graft failure (see [Section 6.8.6](#))
- After HSCT only: Relapse of malignant disease

#### **DAY +1, DAY +7, DAY +15, DAY +22 POST-HSCT**

- Karnofsky PS ( $\geq 16$  years of age); on Days +1, +7 and +15 post-HSCT
- Lansky PS ( $< 16$  years of age); on Days +1, +7 and +15 post-HSCT
- EQ-5D-5L (adult patients only); on Days +7 and +15 post-HSCT
- EQ-5D-Y (pediatric patients and parents [proxy version 1]); on Days +7 and +15 post-HSCT
- Abdominal ultrasound (to assess liver and ascites); on Days +7, +15, and +22 post-HSCT
- \*PK samples (patients randomized to DP arm only); on Days +1, +7, and +15 post-HSCT (see [Sections 6.6.2.1](#) and [6.6.2.2](#) for PK populations and exact time points)
- \*\*Biomarker samples; on Days +7 and +15 post-HSCT (see [Section 6.6.1](#) for exact time points)
- Immunogenicity sample; on Day +15; patients randomized to DP arm only (see [Section 6.7.1](#) for exact time points)

Note: Abdominal ultrasounds can be performed more frequently if VOD is suspected.

\*PK sampling on Day +15 post-HSCT is for patients still receiving defibrotide; PK sample will not be collected if discharge occurs prior to Day +15 post HSCT.

\*\*If hospital discharge occurs prior to Day +15 post-HSCT, then the Day +15 biomarker and ADA samples should be obtained either on the day of discharge or at 1 of the twice weekly visits occurring between early hospital discharge and Day +30 post-HSCT (see [Appendix 1](#)).

Additionally, biomarker and/or PK sampling can be eliminated if investigator believes such sampling will compromise patient safety ([Appendix 6](#)) with the reason for omitting samples clearly documented.

Defibrotide (JZP-381)  
Clinical Trial Protocol: 15-007 Version 4.0

Jazz Pharmaceuticals, Inc.  
20 August 2018

---

